7.2 Study Assessments

For all study days, if a subject has any clinically significant, study-related abnormalities, additional evaluations may be performed at the discretion of the Investigator.

7.2.1 Screening/ Study Visit 1 (Week -2 to -1)

Before any study-specific procedures are performed, the subject must receive an explanation of all study procedures, have an opportunity to ask questions, and must sign and date an Institutional Ethics Committee (IEC) approved written informed consent form.

The following will be conducted at Screening:

- Assess inclusion/exclusion criteria
- Document in the subject's medical records the participation in this clinical trial, that informed consent has been obtained, and that a copy of the signed informed consent form has been given to the subject.
- Prepare subjects for the first treatment period participation by informing them of study restrictions and study procedures
- Record demographics
- Measure height and weight
- Review and record complete medical history (including CV history)
- Record prior and concomitant medications (including all CV medications), including detailed information related to the dose, starting and end dates for all medications. Prior medications taken during the 30 day period before Visit 1 will be collected
- Measure vital signs
- Perform a physical examination
- Perform a standard 12-lead ECG
- Collect clinical laboratory samples: fasting lipid profile, hematology, HbA1c, chemistry, urinalysis, liver safety panel
- Perform serology for hepatitis A, B, and C viruses
- Perform urine pregnancy test (female subjects of childbearing potential only)
- Subjects will continue or begin high intensity statin therapy as described in Section 6.6.

7.2.2 Study Visit 2/Randomization (Week 0)

- Review inclusion and exclusion criteria
- Record any AEs
- Record concomitant medications
- If subject satisfies all inclusion and exclusion criteria, randomization may occur
- Measure vital signs
- Collect clinical laboratory test samples: liver safety panel
- Collect biomarker laboratory test samples in a selected subset of subjects: lipoproteins, fasting insulin, and inflammation panel
- Collect serum/plasma archive samples
- Collect blood samples for pharmacogenomic testing (DNA and RNA) if subject consent received
- Perform MOCA test for any subjects ≥ 70 years of age at randomization
- Administer EQ-5D-5L
- Dispense investigational drug
- Dispense high intensity statin

7.2.3 Study Visits 3-4 (Weeks 2-4)

- Collect clinical laboratory test samples: liver safety panel
- Record concomitant medications
- Monitor AEs
- Perform drug accountability; dispense investigational drug; dispense high intensity statin

7.2.4 Study Visits 5 (Week 6)

- Collect clinical laboratory test samples: liver safety panel
- Collect blood samples for pharmacogenomic testing (RNA only) if subject consent received
- Record concomitant medications
- Monitor AEs
- Perform drug accountability; dispense investigational drug; dispense high intensity statin

7.2.5 Study Visits 6-7 (Weeks 8-10)

- Collect clinical laboratory test samples: liver safety panel
- Record concomitant medications
- Monitor AEs
- Perform drug accountability; dispense investigational drug; dispense high intensity statin

7.2.6 Study Visits 8 (Weeks 12)

- Collect clinical laboratory test samples: liver safety panel
- Collect biomarker laboratory test samples in a selected subset of subjects: inflammation panel
- Collect serum/plasma archive samples
- Record concomitant medications
- Monitor AEs
- Perform drug accountability; dispense investigational drug; dispense high intensity statin

7.2.7 Study Visits 9-10 (Weeks 16-20)

- Collect clinical laboratory test samples: liver safety panel
- Record concomitant medications
- Monitor AEs
- Perform drug accountability; dispense investigational drug; dispense high intensity statin

7.2.8 Study Visit 11 (Week 24)

- Measure vital signs
- Collect clinical laboratory test samples: fasting lipid profile, hematology, HbA1c, chemistry, urinalysis, liver safety panel
- Collect biomarker laboratory test samples in a selected subset of subjects: lipoproteins, fasting insulin
- Administer EQ-5D-5L
- Record concomitant medications
- Monitor AEs
- Perform drug accountability; dispense investigational drug; dispense high intensity statin

7.2.9 Study Visits 12-13 (Weeks 28, 40)

- Collect clinical laboratory test samples: liver safety panel
- Record concomitant medications
- Monitor AEs
- Perform drug accountability; dispense investigational drug; dispense high intensity statin

7.2.10 Study Visit 14 (Week 52)

- Measure vital signs
- Collect clinical laboratory test samples: fasting lipid profile, hematology, HbA1c, chemistry, urinalysis, liver safety panel
- Collect biomarker laboratory test samples in a selected subset of subjects: lipoproteins, fasting insulin, and inflammation panel
- Collect serum/plasma archive samples
- Perform MOCA test for any subjects ≥ 70 years of age at randomization
- Administer EQ-5D-5L
- Record concomitant medications
- Monitor AEs
- Perform drug accountability; dispense investigational drug; dispense high intensity statin

7.2.11 Study Visit 15 (Week 64)

- Collect clinical laboratory test samples: liver safety panel
- Record concomitant medications
- Monitor AEs
- Perform drug accountability; dispense investigational drug; dispense high intensity statin

7.2.12 Study Visit 16 (Week 76)

- Measure vital signs
- Collect clinical laboratory test samples: fasting lipid profile, hematology, HbA1c, chemistry, urinalysis, liver safety panel
- Collect biomarker laboratory test samples in a selected subset of subjects: lipoproteins, fasting insulin
- Administer EQ-5D-5L
- Record concomitant medications
- Monitor AEs
- Perform drug accountability; dispense investigational drug; dispense high intensity statin

7.2.13 Study Visit 17 (Week 88)

- Collect clinical laboratory test samples: liver safety panel
- Record concomitant medications
- Monitor AEs
- Perform drug accountability; dispense investigational drug; dispense high intensity statin

7.2.14 Study Visit 18 (Week 100)

- Measure vital signs
- Perform a physical examination
- Collect clinical laboratory test samples: fasting lipid profile, hematology, HbA1c, chemistry, urinalysis, liver safety panel
- Collect biomarker laboratory test samples in a selected subset of subjects: lipoproteins, fasting insulin
- Perform MOCA test for any subjects ≥ 70 years of age at randomization
- Administer EQ-5D-5L
- Record concomitant medications
- Monitor AEs
- Perform drug accountability; dispense investigational drug; dispense high intensity statin

7.2.15 Study Visit 19 (Week 112) and additional visits until end of study (at 12 week intervals)

- Collect clinical laboratory test samples: liver safety panel
- Record concomitant medications
- Monitor AEs
- Perform drug accountability; dispense investigational drug; dispense high intensity statin

7.2.16 Last Visit on Treatment (at end of study)

- Measure vital signs
- Perform a physical examination
- Collect clinical laboratory test samples: fasting lipid profile, hematology, HbA1c, chemistry, urinalysis, liver safety panel
- Collect biomarker laboratory test samples in a selected subset of subjects: lipoproteins, fasting insulin
- Perform MOCA test for any subjects ≥ 70 years of age at randomization
- Administer EQ-5D-5L
- Record concomitant medications
- Monitor AEs
- Perform final drug accountability for RVX000222; dispense high intensity statin

7.2.17 Follow-up Visit (4 weeks after Last Visit on Treatment) or Early Termination Visit

- Measure vital signs
- Perform a physical examination
- Collect clinical laboratory test samples: fasting lipid profile, hematology, HbA1c, chemistry, urinalysis, liver safety panel
- Collect biomarker laboratory test samples in a selected subset of subjects: lipoproteins, fasting insulin
- Record concomitant medications
- Monitor AEs
- Perform final drug accountability for high intensity statin
- Discharge from study

8.0 SAFETY MONITORING

8.1 Clinical Laboratory Tests

Clinical laboratory blood and urine samples will be collected as described in Section 7.1.4. The Investigator will monitor the laboratory test findings. If any laboratory test on or after first dose is abnormal, it will be followed at the discretion of the Investigator. If the laboratory abnormality induces clinical signs or symptoms, or requires therapeutic intervention, then the diagnosis or medical condition must be entered on the AE eCRF. If the laboratory abnormality is the primary reason for an unforeseen hospitalization or otherwise fulfills the seriousness category of an AE, then the procedure for rapid notification of SAEs must be followed. Likewise, if the laboratory abnormality leads to discontinuation from the study, then the subject must be followed until the abnormality resolves or until it is judged to be permanent.

8.2 Adverse Events

Adverse events that are reported, observed, or elicited by indirect questioning will be collected throughout the study beginning at the time of informed consent and continuing for the duration of the study. Ongoing AEs will be followed to resolution, whenever possible.

8.2.1 Definition of Adverse Events

An AE is any untoward medical occurrence in a subject, which does not necessarily have a causal relationship with study treatment. It includes the appearance or worsening of any undesirable sign, symptom, or medical condition occurring after informed consent even if the event is not considered to be related to study drug. Study drug includes the investigational drug under evaluation and the concomitant statin therapy that is given during any phase of the study.

8.2.2 Methods for Following and Documenting Adverse Events

All subjects are carefully monitored for the occurrence of any AE. The safety variables comprise physical examination findings, vital signs, ECGs, and clinical laboratory tests. Additional safety evaluations considered necessary might be performed at the discretion of the Investigator.

Medical conditions/diseases present before starting study drug are only considered AEs if they worsen after starting study drug. Abnormal laboratory values or test results constitute AEs only if they induce clinical signs or symptoms, are considered clinically significant, or require therapy. Wherever possible, the underlying cause for signs or symptoms should be considered the AE and not the observed signs and symptoms (e.g., pneumonia is preferable to cough, fever, and chest pain). Laboratory values that precipitate dose interruption or discontinuation will be captured as AEs.

The occurrence of AEs should be sought by non-directive questioning of the subject at each visit during the study. Adverse events also may be detected when they are volunteered by the subject during or between visits or through physical examination, laboratory test, or other assessments. All reported AEs are to be recorded in the subject's medical record and in the eCRF. If no AE has occurred during the study period, this should also be indicated in the study documents. The severity and causal relationship to study treatment should be assessed.

Characteristics of the AE are to be recorded including:

- Nature (brief description)
- Time and date of onset
- Time and date of resolution
- Maximum intensity (mild, moderate, severe)
- Seriousness

- Treatment given
- Relationship (causality) to the investigational drug (scale: not related, possibly related, probably related, and related)
- Action taken (investigational drug)
- Relationship (causality) to the concomitant statin therapy
- Action taken (concomitant statin therapy)
- Outcome

8.2.2.1 Follow-up on Adverse Events

Adverse events, abnormal clinical laboratory test results, changes in physical examination findings, or changes in vital sign measurements or ECGs that the Investigator considers to be clinically significant will be followed until resolution or until a stable condition has been established. Subjects withdrawn for safety reasons will be followed until the AE or abnormal laboratory test has been normalized, or until there is an adequate explanation for the AE or laboratory test that is unrelated to the study drug.

8.2.2.2 Rating Scale for Maximum Intensity

Maximum intensity of an AE is the accumulated degree of discomfort, or if the AE is life threatening. Intensity should be assessed according to the following definitions:

- Mild:** Awareness of signs or symptoms, but these are easily tolerated (acceptable)
- Moderate:** Discomfort enough to interfere with usual activity (disturbing)
- Severe:** Incapacity to work or to do usual activity (unacceptable)

8.2.2.3 Rating Scale for Causality

Assessment of causality of suspected AEs is based on associative connections (time or place), pharmacological explanations, previous knowledge of the drug, presence of characteristic clinical or pathological phenomena, exclusion of other causes, and absence of alternative explanations. The Investigator will be asked to assess the causal relationship to the study drug according to the following classifications:

- Not related:** Time relationship with study drug administration is nonexistent or doubtful, or other factors, certain or probable, to have been causative.
- Possible:** Time relationship with study drug administration exists. Other possible causative factors may exist (e.g., concurrent disease or concomitant medication). Improvements on dechallenge or dose reduction (if performed) may or may not have been seen.
- Probable:** Time relationship with study drug administration exists. No other possible causative factors may exist (not reasonably explained by the subject's known clinical state or concomitant medication). Improvements on dechallenge or dose reduction (if performed) have occurred. Recurrence of symptoms on rechallenge (if performed) has occurred. A specific laboratory investigation (if performed) has confirmed the relationship.
- Definite:** Those events for which there is no shadow of doubt that they are a consequence of administration of the study drug. It is likely that such events will be widely documented and generally accepted as having association with the study drug or that they reoccurred after rechallenge (if performed).

8.2.2.4 Follow-up Period After an Adverse Event

If clinically significant findings are present at the study termination (Follow-Up Visit), a determination will be made about each persistent clinically significant finding. If not clinically important (i.e., does not pose a health risk to the subject), the findings will be labeled ongoing and follow-up will cease. If clinically important, follow-up will continue on a case-by-case basis until satisfactory resolution.

8.2.2.5 Coding of Adverse Events

Adverse events will be coded according to the Medical Dictionary for Regulatory Activities (MedDRA). Coding will be performed after the eCRFs have been completed by the Investigative Sites.

8.2.3 Serious Adverse Events

8.2.3.1 Definition

An SAE or reaction is any untoward medical occurrence that at any dose:

- Results in death;
- Is life threatening (life threatening refers to an event in which the subject was at immediate risk of death at the time of the event; it does not refer to an event that hypothetically might have caused death if it were more severe);
- Requires inpatient hospitalization or prolongation of existing hospitalization;
- Results in persistent or significant disability or incapacity;
- Is a congenital anomaly or birth defect; or
- Is medically significant, and though not included in the above list, is an important medical event that may jeopardize the subject or require medical intervention to prevent one of the outcomes listed above. Discontinuation of study drug or conduct of additional diagnostic evaluations, will not, by themselves, satisfy the criterion for a medically significant event.

Medical judgment should be exercised in deciding whether expedited reporting is appropriate in other situations, such as important medical events that may not be immediately life threatening or result in death or hospitalization, but that may jeopardize the subject or may require intervention to prevent one of the other outcomes listed in the definition above. These events should also usually be considered serious. Examples of such events are intensive treatment in an emergency room or at home for allergic bronchospasm, blood dyscrasias, or convulsions that do not result in hospitalization, or development of drug dependency or drug abuse.

8.2.3.2 Hospitalization

Adverse events reported from clinical trials associated with hospitalization or prolongation of hospitalization are considered serious. Any initial admission to a healthcare facility meets these criteria.

Hospitalization does not include the following:

- Rehabilitation facilities
- Hospice facilities
- Respite care
- Skilled nursing facilities
- Nursing home
- Routine emergency room admission
- Same day surgeries (as outpatient/same day/ambulatory procedures)

Hospitalizations or prolongation of hospitalization in the absence of precipitating clinical AE is not in itself an SAE. Examples include:

- Routine treatment or monitoring of the studied indication, not associated with any deterioration in condition
- Elective or pre-planned treatment for a pre-existing condition that is unrelated to the indication under study and has not worsened since the start of study drug
- Treatment on an emergency outpatient basis for an event not fulfilling any of the definitions of a SAE given above and not resulting in hospital admission
- Social reasons and respite care in the absence of any deterioration in the subject's general condition

8.2.3.3 SAE Reporting to Sponsor

All SAEs must be reported, whether or not considered attributable to the study drug, on a separate SAE report form. As much information as possible should be supplied at the time of the initial report with at least the following information:

- Subject, treatment, and study identifiers;
- Investigator's name and address;
- Description of the event, action taken, and outcome;
- Date of onset and current status;
- Any suspect (study) drug, with its start date, dose, and form of administration;
- Reason the AE is regarded as serious;
- Current assessment or opinion of causality;
- Any other available diagnostic information that will contribute to the understanding of the event; and
- If applicable, whether the randomization code has been broken because of the SAE.

The Investigator must inform the Sponsor or Sponsor's designee within 24 hours of when the Investigator is aware of the occurrence of the SAE, whether or not the SAE is related to the study drug. A written report should be submitted, consisting of the SAE report form accompanied by the demographics, medical history, AE, and the concomitant medications pages from the study documents. All pertinent information must be followed by a full follow-up report to the Sponsor within 3 calendar days. As complete a report as possible, (e.g., results of any additional tests) should be forwarded within 8 additional calendar days to the Sponsor. Any significant new information on the SAE and final outcome must be supplied promptly to the Sponsor.

SAEs will be collected throughout the study beginning at Screening and continuing for the duration of the study. Ongoing SAEs will be followed to resolution, whenever possible.

8.2.3.4 Safety Reporting to Investigators, IRBs or IECs, and Regulatory Authorities

The Sponsor will be responsible for reporting all suspected unexpected serious adverse reactions (SUSARs) which do not represent a protocol-defined MACE endpoint (see Section 8.2.3.5), and any other applicable SAEs to regulatory authorities, investigators and IRBs or IECs as applicable, in accordance with national regulations in the countries where the study is conducted.

Relative to the first awareness of the event by/or further provision to the sponsor or sponsor's designee, SUSARs will be submitted to the regulatory authorities as expedited report within 7 days for fatal and life-threatening events and 15 days for other serious events, unless otherwise required by national regulations. The sponsor will also prepare an expedited report for other safety issues where these might materially alter the current benefit-risk assessment of an investigational medicinal product or that would be sufficient to consider changes in the investigational medicinal products administration or in the overall conduct of the trial.

The Investigator should comply with the applicable regulatory requirements related to the reporting of SAEs to the local IEC.

8.2.3.5 MACE Adjudication

All potential primary and secondary MACE events will be reported as SAEs as noted in Section 8.2.3.3. The coronary revascularization cases collected in the eCRF will also be forwarded for adjudication.

An independent, treatment-blinded CEC will be appointed to adjudicate CV events. The Committee will confirm all primary and secondary MACE events as defined below:

Primary and Secondary MACE events will include:

- CV death
- Non-fatal MI
- Hospitalization for CVD events including:
 - Unstable angina
 - Congestive heart failure
 - Any revascularization procedure
- Stroke

All deaths will be adjudicated for CV deaths.

A Charter will be prepared to detail precise responsibilities and procedures applicable to this committee. Adjudications will be based on events as defined in the CEC charter and will be based on the CDISC standardized definitions for Cardiovascular and Stroke Endpoint Events¹.

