9.2 Sample Size

Assuming a design with a provision for futility at 75% adjudicated events will provide approximately 80% power to declare superiority of RVX000222 arm over Placebo with a hazard ratio of 0.7, a true hazard ratio of 1.0 and at an overall 2-sided 5% significance level.

To calculate the sample size, the following additional information was assumed:

- Total number of narrowly defined MACE events needed: 250
- 10.5% event rate in the placebo arm at 18 months
- 30% relative risk reduction (7.47% event rate at 18 months in the RVX000222 arm)
- A cumulative drop-out rate of 10% per arm by the end of the study (5% drop out rate per arm by year one)

With the above design and assumptions, a sample size of 2400 randomized subjects enrolled uniformly over 1.7 years with subjects followed until failure, drop out or end of study will provide the 250 events needed.

The power and sample size for this study was calculated using East 6.2.

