9.7 Safety Analysis

Drug administration, disposition data, medical history and prior medications will be summarized by treatment group using descriptive statistics. Safety data such as clinical laboratory results, vital signs, findings from physical examinations, and MOCAs will be listed and summarized by treatment group where appropriate. For continuous variables, these summaries will include sample size, mean, median, standard deviation, minimum, and maximum. For categorical variables, these summaries will include frequencies and corresponding percentages. No inferential hypothesis testing will be performed on the safety variables.

The assessment of safety will be based on the frequency, intensity, and types of AEs and for change and shift from Baseline in the clinical laboratory variables, and vital sign measurements. Baseline values for clinical laboratory variables, and vital sign measurements are defined as the last non-missing values obtained prior to dosing. Clinical laboratory variables outside reference ranges will be flagged in clinical laboratory listings.

Adverse events will be summarized using the safety set. Adverse events will be coded using MedDRA (version 17.0 or higher), summarized by frequency, severity, relationship to study drug, and number of subjects per treatment and by the preferred term and system organ class. Data will be summarized using preferred term and primary system organ class. The coded events will be summarized by treatment group, in subsets of all treatment-emergent AEs, all treatment-related AEs, non-serious treatment emergent AEs and serious treatment emergent AEs. Adverse events of special interest (opportunistic infections and all serious/severe infections) will be analyzed as a subset of the overall AEs. Treatment-emergent AEs will be defined as any AEs, regardless of relationship to study drug, that occur after the first dose of double-blind investigational drug and within 14 days after the last dose of double-blind investigational drug. Treatment-related AEs will be defined as any AEs that are considered by the investigator to be either possibly, probably, or definitely related to study drug. In addition, if relationship information is missing, the AE will be considered treatment-related. Listings for the subsets of SAEs and treatment-related SAEs will be provided.

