8.1. Adjudication Process of the Key Endpoints

Potential CV events will be identified by comparing all SAE preferred terms to a pre-established list of MedDRA preferred terms. The terms included in the pre-established list are designed to broadly capture

potential CV events from MedDRA SMQs, system organ classes, preferred terms, and lower-level terms specified in the FDA draft guidance document “Endpoints and Standardized Data Collection for Cardiovascular Outcomes Trials”, issued July 22, 2009. All reported terms that code to a listed preferred term will be forwarded to the Clinical Events Committee (CEC) for adjudication. The details of CEC operations and the clinical definitions of the CV outcomes are specified in the CEC charter (v3.0 / 08JUN2017).

High level results of the CEC adjudication of potential CV events as entered into PPD PVG EAS (Electronic Adjudication System) will be transferred and maintained in a SAS dataset. All potential CV events and corresponding adjudication outcomes will be summarized. In addition, association of these events with respect to the primary and key secondary endpoints will be flagged for the analyses. The *possible* adjudication outcomes are categorized as follows:

- Deaths
 - Cardiovascular deaths (including coronary heart disease (CHD) deaths)
 - Non cardiovascular deaths
 - Undetermined cause of death
- Non-fatal cardiovascular events
 - Acute myocardial infarction
 - Hospitalization for unstable angina and evidence of new or progressive obstructive coronary disease.
 - Hospitalization for other angina
 - Hospitalization for heart failure
 - Non- Elective (Urgent/Emergency/Salvage) Coronary Revascularization
 - Stroke

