9.1. Adverse Events

Adverse events will be summarized using the safety set. Adverse events will be coded using MedDRA (version 17.0 or higher), summarized by frequency, severity, relationship to study drug, and number of subjects per treatment and by the preferred term and system organ class. Data will be summarized using preferred term and primary system organ class. The coded events will be summarized by treatment group, in subsets of all treatment-emergent AEs, all treatment-related AEs, and serious treatment emergent AEs.

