9.1.1. Incidence of Adverse Events

A Treatment-Emergent AE (TEAE) will be defined as any AEs, regardless of relationship to study drug, that occur after the first dose of double-blind study drug and within 14 days after the last dose of double-blind study drug. An AE with a reported onset date after the subject has signed the informed consent document and before the date of randomization (or the date of first dose of study drug if a subject was treated but no randomized) will be considered a pre-study event. AEs with missing onset dates will be considered on-study events.

If the day of onset of an AE is missing, and if the month and year of an onset date are on or after Day 1, general imputation rules from [section 4.5](#) will be applied.

If, despite implementing the above conventions, the onset date of the AE cannot be placed before, on, or after Day 1, then the event will be considered on-study.

All AEs will be coded using the MedDRA Version 17.0 or higher coding system. In this dictionary, each diagnosis is mapped to a lower level term and then to a preferred MedDRA term, which is then mapped to a system organ class.

TEAEs will be summarized by treatment group and overall for the SS. Summaries of TEAEs will be displayed by descending overall frequency for system organ class and preferred term. Treatment-Emergent AEs and SAEs will include events per 100 subject-years of study drug exposure. In addition, TEAEs leading to Study Drug Discontinuation, Serious TEAEs and TEAEs resulting in Deaths will be presented.

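### Pooled serious-AE totals by arm include the adjudicated MACE endpoints, so they mix efficacy with safety; a side-by-side summary without confirmed MACE should be added

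*Protocol*

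**What the plan says.** Protocol 8.2.3.5 routes endpoint events through safety reporting: "All potential primary and secondary MACE events will be reported as SAEs as noted in Section 8.2.3.3". The events it lists for adjudication are CV death, non-fatal MI, stroke, and hospitalization for unstable angina, heart failure or revascularization.

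Protocol 9.7 then summarises coded events by arm "in subsets of all treatment-emergent AEs, all treatment-related AEs, non-serious treatment emergent AEs and serious treatment emergent AEs". SAP 9.1 gives nearly the same list: "in subsets of all treatment-emergent AEs, all treatment-related AEs, and serious treatment emergent AEs". SAP 9.1.1 adds that "Treatment-Emergent AEs and SAEs will include events per 100 subject-years of study drug exposure", and also presents fatal treatment-emergent events. The treatment-emergent window runs from first dose to 14 days after last dose.

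Neither document removes CEC-confirmed endpoints from these summaries or adds a version without them. The one place where endpoints are set apart from other serious events is Protocol 8.2.3.4, which concerns expedited reporting of SUSARs, not the analysis.

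The information needed for a split will exist. SAP 8.1 says that "association of these events with respect to the primary and key secondary endpoints will be flagged for the analyses". Section 9 of the SAP does not use that flag.

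**The concern.** Preventing MACE is the trial's hypothesis. If it is true, fewer subjects on RVX000222 will have an SAE for that reason alone. A lower serious-AE total on the drug would then reflect, wholly or partly, the primary endpoint counted a second time, and an equal total could coexist with a somewhat higher frequency of other serious events. If the drug raised MACE, the total would overstate other harm.

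Safety and tolerability is a secondary objective in both documents. Safety is to be described without hypothesis tests (Protocol 9.7, SAP section 9), so readers will rely on these by-arm figures. The plan gives them no overall comparison of serious events that is free of the efficacy outcome.

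**Working it through.** **Inputs from the documents.** Protocol 9.2 assumes a "10.5% event rate in the placebo arm at 18 months", 7.47% at 18 months on RVX000222, 250 events, 2400 subjects entered uniformly over 1.7 years, and 5% drop-out by year one. Allocation is 1:1 (Protocol 6.2), so 1200 per arm. The SAP (4.2) adds a total duration of 2.75 years.

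**Reproducing the plan's figures.** The stated design has "approximately 80% power to declare superiority of RVX000222 arm over Placebo with a hazard ratio of 0.7".
- Rate on RVX000222: 1 − (1 − 0.105)^0.7 = 7.47%, as stated.
- Power with 250 events (Schoenfeld): Φ(√250 × |ln 0.7| / 2 − 1.96) = Φ(0.86) = 80.5%, as stated.
- Yearly hazards: −ln(0.895)/1.5 = 0.0740 (placebo) and −ln(0.9253)/1.5 = 0.0518 (RVX000222); drop-out −ln(0.95) = 0.0513.
- With these hazards, 2.75 years gives 149.0 + 106.5 = 255.5 events. The 250th falls at about 2.70 years, with 145.8 placebo and 104.2 RVX000222 subjects.

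**Gap in narrow MACE.** 145.8/1200 = 12.1% and 104.2/1200 = 8.7%, a difference of 3.5 points. At 18 months it is 10.5 − 7.47 = 3.03 points. As first-event hazards it is 7.4 − 5.2 = 2.2 per 100 subject-years.

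**Effect on the percentage with any SAE.** Let m be the MACE proportion and b the proportion with another SAE. Assume that the two are independent and that b is equal in both arms. Then any SAE = 1 − (1 − b)(1 − m), and the gap between arms is (1 − b)(m_placebo − m_RVX). The excess in b on RVX000222 that would make the totals equal is that gap divided by (1 − m_RVX). The documents give no value for b; 15-25% is assumed.

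| b (assumed) | Any SAE, placebo | Any SAE, RVX000222 | Gap, points | Excess that equalises totals, points |
|---|---|---|---|---|
| 15% | 25.3% | 22.4% | 2.9 | 3.2 |
| 20% | 29.7% | 26.9% | 2.8 | 3.0 |
| 25% | 34.1% | 31.5% | 2.6 | 2.8 |

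**Treatment-emergent window.** The tables count events only up to 14 days after the last dose. If 70% of MACE fall inside that window in each arm (an assumption), m becomes 8.5% and 6.1%. The gap is then 2.1 to 1.8 points and the equalising excess 2.2 to 1.9 points over the same range of b.

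**Smaller effects.** At hazard ratio 0.85 the 18-month RVX000222 rate is 1 − 0.895^0.85 = 9.0%, so the MACE gap is 1.5 points and the any-SAE gap 1.3 to 1.1 points. At hazard ratio 1.0 it is zero, and above 1.0 it changes sign.

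**Not quantified.** Hospitalizations for unstable angina, revascularization and heart failure also enter the SAE totals. The documents give no rates for them.

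**The case against.** The strongest reply is that little is actually hidden. Serious events are tabulated by system organ class as well as preferred term, and a class row is itself a count of subjects. MI, stroke and unstable angina would not ordinarily code to the infection or hepatobiliary classes, so an excess there would stay visible. The protocol analyses opportunistic and serious infections as a subset of their own (9.7), and the DSMB reviews them unblinded (10.8). The liver panel is drawn at every visit, laboratory changes are summarised by arm (SAP 9.2), and laboratory values that lead to interruption or discontinuation are recorded as AEs (Protocol 8.2.2). SAP 8.1 already summarises potential CV events with their adjudicated outcomes, and SAP 9.1.7 reports each death with its cause. MACE is also a legitimate safety outcome, and neither document bases a decision on the SAE total.

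Most of this stands. A reader might infer that the plan conceals infection or liver harm; the documents do not support that. Two limits remain. SAP 9.1 does not repeat the infection subset, and Protocol 9.1 lets the SAP supersede the protocol's methods. Class rows also do not add up to an overall comparison, and reported terms are not adjudicated outcomes, so the split cannot be rebuilt reliably from the cardiac rows.

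A second objection concerns the remedy. It is tempting to drop every event confirmed as a primary or key secondary endpoint. That fails here: all-cause mortality and heart failure hospitalization are key secondary endpoints 8 and 9 (SAP 3.2.2), and undetermined deaths count as CV deaths in the efficacy analysis (SAP 8.2). The fatal table would be emptied, and deaths from infection or liver disease would leave the safety comparison. This objection is correct, and the exclusion must be narrower.

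**Conclusion.** The concern holds for the pooled totals and rates only. As planned, they contain CEC-confirmed endpoints and cannot be read as an endpoint-free comparison of safety.

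Up to about 3 points in the any-SAE percentage is an upper figure for narrow MACE. It rests on the full design effect, on all MACE falling within the treatment-emergent window, and on a 15-25% background of other SAEs independent of MACE. With 70% capture it is about 2 points; without a MACE effect there is no distortion. A reader might take 3 points as the amount of harm that will be masked, but it is what the design assumptions imply, not a prediction. No efficacy estimate, test or stopping decision changes.

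The addition is still worth making. The plan lacks this overall comparison, and fixing the excluded events before unblinding avoids choosing them after the results are known.

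**What to change.** In SAP 9.1.1 and 9.1.4, with a matching sentence in Protocol 9.7:

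- Keep the all-SAE and all-TEAE tables as planned.
- Beside them, add serious TEAE and all-TEAE summaries (subjects, percent, events per 100 subject-years) that exclude only events the CEC confirmed as components of narrow or broad MACE: adjudicated CV death, non-fatal MI, stroke, and qualifying unstable angina or revascularization hospitalization.
- Build the filter from the SAP 8.1 flags together with the adjudicated outcome category, because the endpoint flag alone would also pick up all-cause deaths, heart failure hospitalizations and undetermined deaths.
- Keep non-CV deaths, undetermined-cause deaths, heart failure hospitalizations and potential events that the CEC did not confirm in the safety summary.
- For fatal TEAEs, show adjudicated CV, non-CV and undetermined deaths separately instead of removing any.

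The cost is a short SAP paragraph and a few more tables, run as a filter on existing data. Collection and trial conduct do not change.
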